<SAP Version: 3.0>

---

## 1. INTRODUCTION

### 1.1. RESPONSIBILITIES

This document details the proposed tabular and graphical presentations of data collected from long term cell delivered ribozyme gene transfer product (OZ1) follow up studies; OZ1-HV1-101, OZ1-HV1-102 and OZ1-HV1-202. This document also defines the analysis populations and the safety and efficacy endpoints.

This document has been written by INC based on information contained in the study protocols OZ1-HV1-101 amendment 2 dated 23 October 2007, OZ1-HV1-102 amendment 2 dated 23 October 2007, and OZ1-HV1-202 amendment 2 dated 28 August 2007 and OZ1-HV1-202 amendment 4 dated 07 Jun 2017

The production of summary tables, data listings, graphs and statistical analyses will be the responsibility of Biometrics at INC, and will be performed according to INC standard operating procedures (SOPs).

One completed analysis which was reported in 2011 covered data collected from the point of First Patient First Visit (FPFV) in January 2000 until the last subject year 5 follow-up visit (Last Patient Last Visit: LPLV) in February 2011. A separate Statistical Analysis Plan (SAP) was used for this previous analysis (Kendle study 76803). This previous SAP has also been used as a template for this new INC study (1003733).

This SAP had covered an interim analysis in 2016 and will cover a final analysis happened after DBL of study *OZ1-HV1-202*. The interim analysis in 2016 was based on cumulative data collected from the point of First Patient First Visit (FPFV) in January 2000 until the last subject year 10 follow-up visit (Last Patient Last Visit (LPLV) in February 2016. The final analysis expected in 2018 will be based on cumulative data collected from the point of FPFV in January 2000 until the last subject completes the end of study visit by 30-Nov-2017.

The previous Kendle study (76803) database used TrialBase software and the new INC study (1003733) database will use Oracle Clinical software. Data extracts from each database into SAS will be combined to create analysis datasets covering the cumulative data from both databases. The analyses in 2018 covered in this SAP will also be based on clean data.

<Protocol: Janssen OZ1-HV1-101/102/202>

<INC code: 1003733>

<SAP Version: 3.0>

---

## 1.2. GLOSSARY OF ABBREVIATIONS

AE	Adverse event
CBC	Complete blood count
CD	Cluster of differentiation
CRF	Case report form
FDA	United States Food and Drug Administration
FPFV	First Patient First Visit
HIV	Human immunodeficiency virus
LNL6	Moloney murine leukemia virus based retroviral vector
LPLV	Last Patient Last Visit
MedDRA	Medical Dictionary for Regulatory Activities
n	Number of observations
NSRAE	Non-serious related adverse events
OZ1	Cell delivered rybozyme gene transfer product
PBMC	Peripheral blood mononuclear cells
PCR	Polymerase chain reaction
RCR	Replication competent retrovirus
SAE	Serious adverse event
SAP	Statistical Analysis Plan
SOP	Standard operating procedure

<Protocol: Janssen OZ1-HV1-101/102/202>

<INC code: 1003733>

<SAP Version: 3.0>

### 1.3. DEFINITION OF TERMS

The following terms will be used throughout this statistical analysis plan to refer to the three contributing protocols.

101	OZ1-HV1-101 long term follow-up
102	OZ1-HV1-102 long term follow-up
202	OZ1-HV1-202 long term follow-up

The phrase 'long term follow-up' used throughout this SAP refers to each individual long term follow-up of 101, 102 and 202.

For the purposes of this SAP the term 'adverse events' refers to all serious and non-serious related adverse events only.

All subject ID numbers consist of 6 characters. The following subject ID applies to each of the protocols.

101	0R000X
102	0000XX
202	OZ1XXX

Where X represent the individual subject number.

<Protocol: Janssen OZ1-HV1-101/102/202>

<INC code: 1003733>

<SAP Version: 3.0>

---

## 2. **OBJECTIVES**

1. To undertake long term safety monitoring for any development of:
  - a. Clonal expansion of cells with a predominant OZ1 (*or LNL6 vector*) insertion site
  - b. Insertional oncogenesis
2. To archive/store plasma and peripheral blood mononuclear cells (PBMC) samples for other safety testing that may be required.
3. To assess quantitative marking of the gene transfer product in PBMCs over time. The 202 protocol includes the assessment of quantitative marking and expression of the gene transfer product in PBMCs over time.

<Protocol: Janssen OZ1-HV1-101/102/202>

<INC code: 1003733>

<SAP Version: 3.0>

---

### **3. STUDY DESIGN**

#### **3.1. OVERVIEW OF STUDY DESIGN**

The OZ1-HV1-101, OZ1-HV1-102 and OZ1-HV1-202 studies form the long term follow-up for OZ1. OZ1 comprises a Moloney Murine Leukemia Virus based retroviral vector (LNL6) containing a gene that encodes an anti-human immunodeficiency virus (HIV) ribozyme. It is a recommendation of the United States Food and Drug Administration (FDA) that all individuals receiving retroviral gene transfer products are followed for life.

Patients who participated in the Phase I study “A Marker Study of Therapeutically Transduced CD4+ Peripheral Blood Lymphocytes in HIV discordant twins” were asked to continue long term monitoring under the OZ1-HV1-101 protocol. Patients who participated in the Phase I study “A Phase I Trial of Autologous CD34+ Hematopoietic Progenitor Cells Transduced with an Anti-HIV Ribozyme” were to continued long term monitoring under the OZ1-HV1-102 protocol. Patients who participated in the Phase II study “A randomized Phase II, double blind, controlled trial to evaluate the safety and efficacy of autologous CD34+ hematopoietic progenitor cells transduced with placebo or an anti-HIV ribozyme (OZ1) in patients with HIV-1 infection” continue long term monitoring under the OZ1-HV1-202 protocol. Following completion and unblinding of the Phase II study, patients who were identified as having been enrolled in the placebo arm were subsequently discontinued from the long term follow-up study 202.

All patients in each protocol will be reviewed at 6 month intervals (+/- 6 weeks) until year 5 post infusion. Thereafter, all patients will be reviewed annually (+/- 12 weeks) on the anniversary of their infusion. Given the recommendation to follow patients for life, patients who withdraw from the study or have been lost to follow-up but return for assessments at a later time may be re-instated in their study. Additional unscheduled visits may be made if any clinical or biological findings require further investigation. A schedule detailing the timing of the follow-up visits and the procedures carried out at each visit is presented in Table 1.

Various data and samples have been collected under previous protocol versions. For data consistency across all the long term follow-up protocols only data corresponding to the schedule presented in Table 1 collected on one standardized Case Report Form (CRF) will be included in the data analysis. Additionally, the CRF will collect ‘Initial Study Information’ which will comprise of demography, significant medical history, treatment details from the respective original studies, and PBMC analysis and complete blood count (CBC)/differential and platelets results obtained 2 years post infusion or the nearest timepoint before starting the respective long term follow-up if 2 years post infusion data is not available.

<Protocol: Janssen OZ1-HV1-101/102/202>

<INC code: 1003733>

<SAP Version: 3.0>

**Table 1 Visit Schedule**

Follow-up Visit	Year 2.5	Year 3	Year 3.5	Year 4	Year 4.5	Annual Visit Year 5-15	Annual Visit Year 15+
Clinical history and examination	X	X	X	X	X	X	X
Complete Blood Count (CBC)/Differential and Platelets	X	X	X	X	X	X	
Plasma archive		X		X		X	X
PBMC archive 		X		X		X	X
OZ1 integration site polymerase chain reaction (PCR) 	X	X	X	X	X	X	
Adverse Events Assessments	X	X	X	X	X	X	X
Contact details updated for patient and nominated secondary contact	X	X	X	X	X	X	X

The PBMCs will be stored as cryopreserved cells and cell pellets for replication competent retrovirus (RCR) and other safety testing as required.

This includes both marking (quantitative OZ1/LNL6 DNA-PCR) and the detection of predominant integration sites. If the percentage of cells marked by the vector (quantitative OZ1/LNL6 DNA-PCR) is less than 1% of the test cell population, the site of integration will not be investigated. If a predominant integration site is detected, the patient will be retested within 3 months to determine if it persists. If so, the site of integration of OZ1 will be sequenced and mapped to the human genome to determine any association with known human oncogene. In all instances that a predominant integration site is present and, particularly when there is expansion of a cellular clone, the patient will be monitored for signs of cancer, so that treatment can be initiated as early as possible. Ongoing analysis of quantitative marking of the gene transfer product will be performed as part of the testing of predominant integration sites. These marking data will also be analyzed independently to detect any changes in the number of cells carrying the gene transfer product.

Blood can be collected up to 1 week prior to the other assessments.

<Protocol: Janssen OZ1-HV1-101/102/202>

<INC code: 1003733>

<SAP Version: 3.0>

**Table 2 Visit Schedule (Study 202)**

Follow up visit	Yr 2.5	Yr 3	Yr 3.5	Yr 4	Yr 4.5	Annual Yr 5+ /End-of-Study 
Clinical history and examination	X	X	X	X	X	X
Complete Blood Count/Differential and Platelets	X	X	X	X	X	X
Plasma archive		X		X		X
PBMC archive 		X		X		X
OZ1 integration site (PCR) 	X	X	X	X	X	X
Adverse Events Assessment	X	X	X	X	X	X
Contact details updated for subject and nominated secondary contact	X	X	X	X	X	X
Volume of blood drawn at visit (ml)	30	73	30	73	30	73

The PBMCs will be stored as cryopreserved cells and cell pellets for assessment of replication competent retrovirus (RCR) and other safety testing as required.

<Protocol: Janssen OZ1-HV1-101/102/202>

<INC code: 1003733>

<SAP Version: 3.0>

---

This includes both marking (quantitative OZ1/LNL6 DNA-PCR) and the detection of predominant integration sites. If the percentage of cells marked by the vector (quantitative OZ1/LNL6 DNA-PCR) is less than 1% of the test cell population, the site of integration will not be investigated. If a predominant OZ1 integration site is detected, the patient will be retested within 3 months to determine if it persists. If so, the site of integration of OZ1 will be sequenced and mapped to the human genome to determine any association with a known human oncogene. In all instances that a predominant integration site is present and, particularly when there is expansion of a cellular clone, the patient will be monitored for signs of cancer, so that treatment can be initiated as early as possible. Ongoing analysis of quantitative marking of the gene transfer product will be performed as part of the testing of predominant integration sites. These marking data will also be analyzed independently to detect any changes in the number of cells carrying the gene transfer product.

Blood can be collected up to 1 week prior to the other assessments.

 End-of-Study assessments will be performed after all ongoing patients have been followed up for least 10 years post-infusion. End-of-Study visits will be completed by 30 November 2017. In the event that a patient cannot attend a site visit, telephonic follow-up will be an acceptable alternative.

<Protocol: Janssen OZ1-HV1-101/102/202>

<INC code: 1003733>

<SAP Version: 3.0>

---

### **3.2. STUDY SAMPLE SIZE**

The sample size of the long term follow-up studies is dependant on the number of patients continuing into the long term follow-up phase from the original studies. No formal sample size calculation was performed.

<Protocol: Janssen OZ1-HV1-101/102/202>

<INC code: 1003733>

<SAP Version: 3.0>

## **4. POPULATIONS FOR ANALYSIS**

Assignment of patients to each of the populations together with a review of the data will take place at a Data Review Meeting to be held immediately prior to database lock. All decisions taken at the Data Review Meeting regarding the analysis populations will be fully documented.

The following listings will be provided for the Data Review Meeting:

Demography	(Listing 16.2.2)
Significant Medical History	(Listing 16.2.3)
Treatment Details	(Listing 16.2.4)
PBMC Analysis	(Listings 16.2.5.1, 16.2.5.2, 16.2.5.3)
Patient Disposition	(Listing 16.2.1.1)
Clinical History	(Listing 16.2.12)
Discontinuation Details	(Listing 16.2.1.2)
Re-instatement Details	(Listing 16.2.1.3)
Adverse Events	(Listings 16.2.8.2, 16.2.8.3)
Death	(Listing 16.2.8.1)
Proposed analysis Populations together with reasons for exclusion	(Listing 16.2.1.4)

Other listings may be provided for the Data Review Meeting as required.

### **4.1. SAFETY POPULATION**

The Safety population will consist of any patient who was enrolled in either of the OZ1-HV1-101, OZ1-HV1-102 or OZ1-HV1-202 studies and continued into the respective long term follow-up protocol.

### **4.2. PER-PROTOCOL POPULATION**

All patients who are eligible for inclusion in the Safety population and received OZ1 or LNL6 or combination OZ1/LNL6.

<Protocol: Janssen OZ1-HV1-101/102/202>

<INC code: 1003733>

<SAP Version: 3.0>

---

## 5. OVERALL CONSIDERATIONS

All summary tables and data listings produced by INC will use the statistical package SAS (v9.2 or a more recent version).

In general, categorical data will be presented using counts and percentages, whilst continuous data will be presented using the descriptive statistics, mean, standard deviation (SD), median, minimum, maximum and number of patients with an observation (n). Minimum and maximum values will be quoted to the number of decimal places as recorded on the CRF; means, medians and SDs will be quoted to one further decimal place. Percentages will be rounded to one decimal place. Percentages smaller than 0.1 will be presented as <0.1. Percentages whose numerator is zero will be reported as zero.

All data recorded on the Case Report Form (CRF) and any derived data will be listed for all patients.

The Safety population will be used to present Adverse Event and death data. The PP population will be used to present all data .

Unless otherwise stated missing data will not be imputed. Patients who withdraw prematurely will have their data summarized at the last attended visit. Repeat assessments will not be summarized unless otherwise indicated but will be fully listed. Similarly, data collected at unscheduled visits will be listed only. Repeat and unscheduled visits will be identified on the data listings.

Where of interest, presentation of data will be pooled to reflect the target cell type, CD4 cells in OZ1-HV1-101 and CD34 cells in OZ1-HV1-102 and OZ1-HV1-202 in addition to presenting separately and overall.

<Protocol: Janssen OZ1-HV1-101/102/202>

<INC code: 1003733>

<SAP Version: 3.0>

---

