This will be a follow-up study of patients previously enrolled in the OTH/OZ1-INT-1 trial. All patients in this protocol will be reviewed at six monthly intervals until year 5 post infusion. Thereafter all patients will be reviewed annually, on the anniversary of the infusion until withdrawal or study completion. Patients who were enrolled in the placebo arm will be discontinued after OTH/OZ1-INT-1 has been unblinded.

STUDY POPULATION

Participants in the OTH/OZ1-INT-1 Phase II study entitled “A Randomized Phase II, double blind, controlled trial to evaluate the safety and efficacy of autologous CD34+ hematopoietic progenitor cells transduced with placebo or an anti-HIV-1 ribozyme (OZ1) in patients with HIV-1 infection” will be asked to consent to continue safety monitoring and gene marking as described in this protocol.

DOSAGE AND ADMINISTRATION

All participants of the OTH/OZ1-INT-1 Phase II study received a single dose of placebo or OZ1 transduced CD34+ cells.

SAFETY EVALUATIONS†

Follow-up will be conducted as per current FDA/Center for Biologics Evaluation and Research (CBER) recommendations. Evaluations will include monitoring for related adverse events such as the development of replication competent retrovirus (RCR), predominant integration sites and insertional oncogenesis. Blood samples will be collected for archival storage for assessment of replication competent retrovirus (RCR) and other safety testing as necessary.

EFFICACY EVALUATIONS

Ongoing analysis of quantitative marking of the gene transfer product (OZ1 and LNL6) in peripheral blood mononuclear cells (PBMC) will be performed as part of the testing of predominant integration sites. These marking data will also be analyzed independently of the integration analysis to detect changes in the number of cells carrying the gene transfer product.

TIME AND EVENTS SCHEDULE

Follow up visits may be part of routine clinic visits where possible, but must be performed as described in the Time and Events Schedule. Additional unscheduled visits will be made if clinical or biological findings, as described in this protocol, require additional evaluation or investigation or as directed by the Investigator.

OZ1: Clinical Protocol OZ1-HV1-202 Amendment 4; 07 June 2017

TIME AND EVENTS SCHEDULE[†]

Follow up visit	Yr 2.5	Yr 3	Yr 3.5	Yr 4	Yr 4.5	Annual Yr 5+ /End-of- Study ⁴
Clinical history and examination	X	X	X	X	X	X
Complete Blood Count/Differential and Platelets	X	X	X	X	X	X
Plasma archive		X		X		X

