10.2 Procedures

NON-SERIOUS ADVERSE EVENTS

Non-serious adverse events must be recorded using medical terminology in the source document and in the case report form if they have a possible, probable or very likely suspect association to the study drug.

SERIOUS ADVERSE EVENTS

All adverse events meeting the definition of serious, regardless of severity or presumed relationship, must be recorded using medical terminology in the source document and in the case report form. Only SAEs that are “possibly”, “probably” or “very likely” related to the study drug must be reported using the Sponsor Serious Adverse Event Form within 24 hours of knowledge of the event. Exceptions to this include:

- Death, regardless of the cause, is considered a reportable SAE;
- Malignancy (except Basal Cell or Squamous Cell Carcinomas), regardless of causality, is considered a reportable SAE.

Whenever possible, diagnoses should be given when signs and symptoms are due to a common etiology (e.g. cough, runny nose, sneezing, sore throat, and head congestion should be reported as “upper respiratory infection”). Investigators must record in the CRF their opinion concerning the relationship of the SAE to study therapy. All measures required for serious adverse event management must be recorded in the source document.

OZ1: Clinical Protocol OZ1-HV1-202 Amendment 4; 07 June 2017

Subjects (or their designees, if appropriate) must be provided with a “study card” indicating the name of the investigational product, the study number, the investigator’s name, and a 24-hour emergency contact number.

All reportable SAEs occurring during the study period must be reported to the appropriate sponsor contact person by investigational staff within 24 hours of their knowledge of the event. If the SAE is a death or a life threatening event the Investigator must notify the Sponsor immediately by both telephone and FAX.

Information regarding serious adverse events will be transmitted to the sponsor using the Sponsor Serious Adverse Event Form, which must be signed by a member of the investigational staff. The initial report of a serious adverse event may be made by facsimile (fax) or telephone. It is preferable that serious adverse events be reported via fax. Subsequent to a telephone report of a serious adverse event, a Serious Adverse Event Form must be completed by the investigational staff and transmitted to the sponsor within 24 hours.

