Appendix 2:[†]
TELEPHONE FOLLOW-UP QUESTIONNAIRE
FOR SEMI-ANNUAL, ANNUAL, OR END-OF-STUDY REVIEW OF CLINICAL HISTORY

Instructions for Interviewer: This interview will be conducted over the phone by a study investigator only if a patient is unable to be reviewed in the clinic.

SUBJECT NAME:

Date of Birth: |__|_| - |__|_|_|_| - |__|_|
 DD MMM YY

INTERVIEWER SIGNATURE:

Date of Interview: |__|_| - |__|_|_|_| - |__|_|
 DD MMM YY

Study Physician: Circle all appropriate answers for PARTS A, B & C. If respondent answers 'yes' to any of the PART A questions, complete sub-sections and add any additional comments.

All questions refer to the time since the since the last study visit or interview.

PART A: Targeted Review of Clinical History

Please elicit a history to determine whether the subject currently has or has experienced any of the following diseases/conditions (new or exacerbation of existing) since the last review.

Disease, condition or problem	Approximately when did they FIRST notice this condition?	Over the past 12 months have they seen a health care provider for this condition?	Over the past 12 months, have they been hospitalized for this condition?	Study Physician's Comments including Diagnosis

1. New or exacerbated hematologic disorders including laboratory abnormalities?
 
 No (skip to Q2)
 
 Yes
	

 
 dd mm yy 
	
No.....
 
Yes...
	
No
 
Yes: (record hospital name)
	
.....
 
.....
 
.....

2. New malignancies including skin cancer?
 
 No (skip to Q3)
 
 Yes
	

 
 dd mm yy 
	
No.....
 
Yes...
	
No
 
Yes: (record hospital name)
	
.....
 
.....
 
.....

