### **8.5. CLINICAL HISTORY**

Individual patient responses (Yes/No/Not Assessed) to the following questions will be recorded at 2.5 years post infusion and all subsequent follow-up visits:

Has the patient,

experienced new or exacerbated haematological disorders (including clinically significant laboratory abnormalities)?

<Protocol: Janssen OZ1-HV1-101/102/202>

<INC code: 1003733>

<SAP Version: 3.0>

---

had any new malignancies (including skin cancers)?

been exposed to possible therapeutic or environmental mutagenic agents?

experienced new or exacerbated pre-existing immunological/rheumatologic disorders?

experienced new or exacerbated pre-existing neurological disorders?

undergone a biopsy or surgical removal of a tumour?

For the last question, patient response to 'Was a sample collected for study assessment?' (Yes/No) will be recorded. If the response is 'Yes', the date of collection, will also be recorded. For the preceding questions, patient response to 'Is this possibly related to the gene transfer product will also be recorded?'

The number and percentage of patients responding 'yes' to the above questions will be tabulated and presented by whether the information was received at a clinical visit, by telephone contact, and overall. The number of patients with clinical history information will also be presented. Percentages within each follow-up visit will be calculated using the number of patients with clinical history information at that visit.

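### Findings first recorded at unscheduled or repeat assessments can be missing from the blood count and clinical history tables (14.5.X and 14.4.x), though not from the adverse event and death tables

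*SAP*

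**What the plan says.** SAP section 5 (Overall Considerations) sets the rule for data collected outside the visit schedule. For repeats: "Repeat assessments will not be summarized unless otherwise indicated but will be fully listed". For extra visits: "Similarly, data collected at unscheduled visits will be listed only". The first sentence leaves room for exceptions; the second does not. The same paragraph adds that "Repeat and unscheduled visits will be identified on the data listings". SAP section 3.1 points the same way: "only data corresponding to the schedule presented in Table 1 collected on one standardized Case Report Form (CRF) will be included in the data analysis".

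The Protocol Synopsis explains why such visits happen: "Additional unscheduled visits will be made if clinical or biological findings, as described in this protocol, require additional evaluation or investigation". Protocol section 7.1 (Unscheduled Assessments) and SAP section 3.1 give similar triggers.

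Clinical history is tabulated visit by visit. SAP section 8.5 says: "Percentages within each follow-up visit will be calculated using the number of patients with clinical history information at that visit". The shells for Tables 14.4.x and 14.5.X have one row block per scheduled post-infusion visit.

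Adverse events follow a different route. SAP section 8.2 collects serious events and non-serious related events throughout follow-up, and counts them by event and by patient. Under Protocol section 10.2, non-serious events are entered "in the case report form if they have a possible, probable or very likely suspect association to the study drug".

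**The concern.** Leaving unscheduled values out of by-visit means is ordinary practice, because it keeps each row to one comparable observation per patient. The difficulty arises when no other table picks the values up. Here the visits are prompted by findings, so what is left out is not a random sample of the data. This is a safety follow-up whose purpose is to detect delayed events: malignancy and haematologic, autoimmune and neurologic disorders. A reader who relies on the tables could see milder extremes of blood count, or fewer patients with a new disorder, than the database holds. Protocol section 9.2 also commits to both listing and tabulating clinical history and blood counts.

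**Working it through.** The plan gives no figure to reproduce: SAP section 3.2 reports no sample size calculation, and Protocol section 9 makes the analysis mainly descriptive. The check traces a finding made at an unscheduled visit through each safety output.

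**1. Adverse events and deaths (Tables 14.3.x).** SAP section 8.2 does not tie inclusion to a scheduled visit. A serious event, or a non-serious related one, first seen at an unscheduled visit is therefore counted. Section 8.2 names malignancy among the serious events, Table 14.3.2 counts a patient once within each system organ class and preferred term, and deaths go to Table 14.3.6. Read literally, however, SAP section 5 makes no exception for these data. The specific text of section 8.2 should prevail, but the SAP does not say so.

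**2. Blood counts (Table 14.5.X).** SAP section 8.4 and the shell give results and change from baseline by visit, with no worst-value row.
- If the abnormal count is the scheduled one, it stays in the table and only the follow-up draw is confined to the listing.
- If the extreme value is first seen at an unscheduled or repeat draw, it is absent. A later scheduled value does not restore it, and a review by telephone yields no count.

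**3. Clinical history (Tables 14.4.x).** A disorder goes untabulated only if all of the following hold:
- it is non-serious and judged unrelated, so Protocol section 10.2 and SAP section 8.2 keep it out of the adverse event data;
- it is recorded at an unscheduled visit;
- it is not reported again at the next scheduled review.

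On the last condition, the telephone form in Protocol Appendix 2 is ambiguous. One line reads: "All questions refer to the time since the since the last study visit or interview". If an unscheduled visit counts as a study visit, 'no' is then a correct answer at the next call. Another line in the same form sets the reference point at the last review, which would recover the event.

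Basal and squamous cell carcinomas may belong in this group. Protocol section 10.2 exempts them from the rule that malignancy is reportable whatever its cause. SAP section 8.2 lists malignancy as serious without that exception, and SAP section 8.5 includes skin cancers in its malignancy question. Their classification as adverse events is therefore unclear.

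**4. Time between scheduled reviews.** Visits are anchored to the infusion date. Protocol section 4 and Table 3 allow ±12 weeks around the annual visit, so one visit 12 weeks early followed by one 12 weeks late gives 52 + 12 + 12 = 76 weeks. Findings can arise at unscheduled visits anywhere in that interval.

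**5. Distinct patients.** The 'Overall' column in the 14.4.x shells combines clinic and telephone contacts, not visits over time, and each row has its own denominator. Rows cannot be added: one 'yes' in each of the six annual rows from year 5 to year 10 could come from anywhere between one and six patients.

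**6. Weight of one patient.** Protocol section 1.1 says about half of 74 patients received OZ1, so about 37. If all were followed, one omitted patient is 1/37 = 2.7 percentage points within study 202, and more at visits with fewer attending. The 14.4.x shells pool all three studies, so the share there depends on a per-visit denominator that the documents do not give.

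**The case against.** The strongest reply is that little is lost. Every item is listed, unscheduled records are flagged, and with a few dozen patients in study 202 Listings 16.2.11 and 16.2.12 can be read patient by patient. No passage says that the clinical history questions are completed at unscheduled visits; if they are not, nothing is dropped and the next scheduled review can capture the event. The telephone form is used only when a clinic review is impossible, and the SAP's questions for clinic visits state no recall limit. SAP section 5 also says that early withdrawals are summarised at their last attended visit. All of this stands, and it limits the gap in Tables 14.4.x to a possibility. The withdrawal sentence does not settle the matter, because it conflicts with the unscheduled-visit rule when the last attended visit was unscheduled.

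A reader might infer several stronger things that the documents do not support:
- *Every safety summary omits these data.* Tables 14.3.x do not depend on visits.
- *Malignancies disappear.* SAP section 8.2 counts malignancy as serious; only the two skin carcinomas are in doubt.
- *A patient who dies or is lost before the next review is never counted.* Deaths from any cause are reportable and tabulated, and earlier serious events remain in the tables.
- *The worst blood counts are removed.* Only extremes first seen at an unscheduled or repeat draw are.

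What the reply does not remove is that Table 14.5.X has no worst-value row, and that no table counts the patients who ever had a non-serious, unrelated disorder.

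**Conclusion.** The point holds in a limited form. The rule in SAP section 5 selectively leaves out data prompted by findings, and two kinds of result can then be tabulated nowhere: extreme blood counts first seen off schedule, and non-serious, unrelated disorders recorded only off schedule and not reported again. The first follows directly from the rule and the shell. The second rests on three assumptions: that clinical history is recorded at unscheduled visits, that the next scheduled review does not repeat the answer, and, for the two skin carcinomas, that they are classed as non-serious. The lack of a distinct-patient count in Tables 14.4.x needs no assumption.

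Any effect would make these tables look milder than the data, but its size is unknown: the documents do not show whether any such finding occurred. Because the listings keep everything, this is a worthwhile small improvement to the tables and not a failure of safety monitoring.

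**What to change.** Three changes to the SAP:

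- **Section 5.** State that the unscheduled-visit rule does not apply to adverse events or deaths. Add that visit rows use scheduled visits, while unscheduled and repeat data contribute to any-time rows. Align the data-scope sentence in section 3.1 with this.
- **Tables 14.4.1 to 14.4.6.** Add a row 'Any time in long-term follow-up (scheduled, unscheduled or telephone)', counting each patient once.
- **Each Table 14.5.X.** Add summaries of the lowest and highest post-baseline value per patient, using all visits.

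The cost is SAP wording and a few derived rows from data already collected and listed; no new data collection is needed. The worst-value rows will look somewhat more extreme because they include event-triggered draws, and a footnote should say so.
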